9.5 Criteria for Removal from Protocol Treatment

All reasons for discontinuation of treatment must be documented. All patients will be followed until death or 5 years post treatment (whichever time point comes first). If protocol treatment is discontinued for any reason other death, follow up and data collection will continue as specified in the protocol.

Subjects will be removed from therapy when any of the criteria listed in Section 9.5 apply. Notify the Principal Investigator, and document the reason for treatment discontinuation and the date of discontinuation. The subject should be followed-up per protocol.

Subjects can be taken off the study treatment and/or study at any time at their own request, or they may be withdrawn at the discretion of the investigator for safety, behavioral or administrative reasons. The reason(s) for discontinuation will be documented and may include:

- 9.5.1 Subject voluntarily withdraws from treatment (follow-up permitted);
- 9.5.2 Subject withdraws consent (termination of treatment and follow-up);
- 9.5.3 Subject is unable to comply with protocol requirements;
- 9.5.4 Subject demonstrates disease progression (unless continued treatment with study drug/treatment is deemed appropriate at the discretion of the investigator);
- 9.5.5 Subject experiences toxicity that makes continuation in the protocol unsafe;
- 9.5.6 Treating physician judges continuation on the study would not be in the subject's best interest;
- 9.5.7 Subject becomes pregnant (pregnancy to be reported along same timelines as a serious adverse event);

- 9.5.8 Development of second malignancy (except for basal cell carcinoma or squamous cell carcinoma of the skin) that requires treatment, which would interfere with this study;
- 9.5.9 Lost to follow-up.
- **9.5.10** Unacceptable toxicity.
- **9.5.11** A greater than two week delay in protocol treatment, as specified in Sections 6.0.
- **9.5.12** Development of intercurrent, non–cancer-related illnesses that prevent either continuation of therapy or regular follow-up.

9.6 Other response parameters

- **9.6.1** Time to Local Progression: The time to progression will be measured from the date of study enrollment to the date of documented local progression as determined by clinical exam and imaging studies.
- **9.6.2** Overall Survival: The survival time will be measured from the date of study enrollment to the date of death. All patients will be followed for survival. Every effort should be made to document the cause of death.
- **9.6.3** Progression Free Survival: Progression free survival will be measured from the date of study enrollment to the date occurrence of local or regional progression, distant metastases, or death from any cause.

9.7 Comorbidity Data and Rating

The Charlson Comorbidity index will be used to assess pretreatment comorbidity status (see Appendix V).

9.8 Cost-Effectiveness

Health care utilization data needed to assess costs will be obtained at the baseline visit (for the prior one year period) and at each follow-up visit (see Appendix II). Questions will be asked for the utilization of all the health care services (see Appendix VI). The health utilization data will be collected at each study site. They will be transferred to the data management center located at the Department of Epidemiology and Biostatistics, Texas A&M Health Science Center (TAMHSC). At TAMHSC, a designated staff member will be responsible for calling each health service provider and obtain the bills that are associated with each service reported in the CRF, with costs calculated using methods outlined below and stored in a designated computer for analysis purpose. Patients will be given a diary at the beginning of the study to aid in recording all health related visits and expenditures. Additionally, in order to assess the treatment related indirect costs and patient out of pocket costs, a form will be administered during the last week of treatment or at the first available follow up visit after completion of radiation treatment (see Appendix VII).

Hospitalizations: Inpatient admissions (hospitalizations for any reason) with dates of admission and discharge and name of hospital. Patient bills (UB-04s) also will be obtained for each hospitalization. Inpatient facility costs will be estimated by total billed charges adjusted by a facility-specific cost-to-charge ration from Medicare Cost Reports. We also will attempt to obtain billing records for inpatient physician services. For hospitalizations with physician billing records, impatient physician costs will be estimated by applying Medicare payment rates under the RBRVS-based Medicare Fee Schedule to billed procedures in the physician billing records. For hospitalizations where physician billing records are not available, inpatient physician costs will be estimated using a multivariate regression model from data that combines Medicare inpatient and physician bills. This is to

be accomplished by merging the Medicare Provider Analysis and Review (MEDPAR) data set (a file that contains a record for each discharge of a Medicare beneficiary) and the 5 percent sample file of Medicare claims for physician services in the Medicare Beneficiary Survey. We will calculate the ratio between hospital costs and physician-allowable charges. Separate regression models will be estimated for all lung-related admissions (e.g., DRG 082) and for all other admissions. These regression models will be used to predict the ratio of inpatient physician costs to hospital costs for each admission. This predicted ratio multiplied by the hospital costs will be the estimated physician costs for the admission, but only for admissions without inpatient billing information.

Treatment Cost: Direct costs of radiation treatment including consultation, simulation, treatment planning, and treatment delivery. Patient bills related to treatment will be obtained and estimated by total billed charges adjusted by facility-specific cost-to-charge ration from Medicare cost reports as described above.

Emergency Room visits: The date of ER visit and name of the facility, and whether the ER visit resulted in a hospital admission. ER costs will be estimated using Medicare average payment rates for facility and physician charges, using the merged MEDPAR and MBS data as described above.

Physician and Clinic Visits: The date of the visit, the name of the physician or physician clinic, and the service provided (physician exam, lab test, physical therapy, etc.). Costs for physician and clinic visits will be calculated based on billing records obtained for such visits, using Medicare payment rates for procedures indicated in the clinic billing records.

Prescription Medications: Prescription drugs used, including dosage strength and frequency of administration. Information about name, dose, and frequency of all prescription medications will be recorded. The medications used by the study patients will be assigned an NDC drug code. Unit costs for these drugs will be estimated as the "AWP" price published in the Red Book less 15%. Outpatient drug costs will be calculated by multiplying unit cost by the number of pills used per day times the length of time the patient received the medication. The length of time a patient took a medication will be estimated by assuming that if a medication is not listed on the CRF for a follow-up visit, use was discontinued at the mid-point of the interval since the prior CRF assessment. Note that costs of drugs administered through a clinic (e.g., reimbursed under Medicare Part B) are included under "clinic visit costs" and impatient drug costs are included under "inpatient facility costs."

Home Health Care: The number of home health care visits will be recorded. Costs for home care visits will be calculated based on Medicare payment rates for home health care.

9.9 Health-Related Quality of Life (HRQOL) Analysis

The study design is to prospectively analyze the QOL among patients with stage III NSCLC randomized between standard radiotherapy (60 Gy) versus hypofractionated IGRT radiation therapy. While hypofractionation is hypothesized to yield greater tumor cell kill, it may also increase the normal tissue toxicity, in which case there may be a decrease in HRQOL. The primary normal tissue toxicities in patients receiving radiation for lung cancer are esophagitis and pneumonitis. Prior studies have demonstrated that the most sensitive and clinically meaningful method for accurately capturing the normal tissue toxicities is via patients reported outcomes (PROs), such as HRQOL.

In this randomized trial, we plan to assess the FACT-TOI in all arms at 4 specific

time points to minimize patient burden: baseline (pretreatment), at the end of treatment (last day of treatment), and at the 6 and 12 month follow ups (See Appendix II). In order to analyze the difference in QOL between all arms, we plan to use a brief, validated instrument that is user friendly and has clinical relevance (the Lung Cancer Subscale of the FACT-TOI). FACT-TOI is a measure that sums the functional well being (FWB), physical well being (PWB), and the lung cancer subscale (LCS) of the Functional Assessment of Cancer Therapy - Lung (FACT-L) QOL instrument, which has been extensively used for measuring QOL in patients with lung cancer.[31] In a review of the literature reported that the FACT-L scale has been used in more than 5,000 patients and has been found to be sensitive to changes in performance status, treatment response.[32] FACT has been translated into 26 languages and is available free of charge to institutions with the completion of an agreement to share data, accessible at

http://www.facit.org/translation/licensure.aspx. The full FACT-L questionnaire can be completed in less than 10 minutes. This instrument has not only been shown to be prognostic for survival, but also sensitive to changes in QOL on serial evaluations throughout treatment. Importantly, the FACT-TOI has been associated with clinically meaningful changes in

patients with lung cancer.[33] The lung cancer sub-scale (LCS) consists of 9 items, involving lung cancer specific symptoms. All items are rated on a 5 item (point) Likert Scale, from 0 (not at all) to 4 (very much). It has been determined that a 3-point difference on the FACT-G subscales is associated with a meaningful difference in clinical and subjective indicators. Thus, a difference of 3 LCS points will be considered clinically significant. As the LCS focuses on lung cancer

symptoms, this will be used for the primary endpoint; however, the more general subscales of physical and functional well-being (on the brief FACT-TOI) will also be collected. See Appendix VIII for the appropriate forms.

In addition, the EQ-5D health related quality of life questionnaire will be used as well. EQ-5D is a standardized instrument for use as a measure of health outcome. Applicable to a wide range of health conditions and treatments, it provides a simple descriptive profile and a single index value for health status. The US version of the EQ-5D will be used, to enable mapping of general HR-QoL scores from EQ-5D scores into health state utility scores (ranging from 0 to 1) for the US population. These utility scores are needed for cost-utility analysis (estimates of costs per "quality adjusted" life-year gained). See Appendix IX for the appropriate forms.

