7.0 Drug Therapy

At the treating physician's discretion, chemotherapy may be administered concurrently ONLY to patients enrolled on the standard arm (30 fractions) using a combination of carboplatin and paclitaxel (Taxol) with standard dosing for concurrent chemo-radiotherapy in lung cancer. Patients treated on this arm, however, may not receive any other chemotherapy regimens, targeted therapy, or drugs known to act as radiosensitizers. Patients on the experimental arm (15 fractions) may NOT receive any concurrent chemotherapy, targeted therapy or drugs known to act as radiosensisitizers. Patients on either arm of the study may go on to receive adjuvant chemotherapy if determined appropriate by their medical oncologist one week after completing radiation therapy.

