11.5.1 Overall Survival

Overall survival time will be estimated using the Kaplan-Meier approach. The stratified log-rank test will be used to test for a statistically significant difference in survival distributions. The null and alternative hypotheses are H_0 : $S_1(t) < S_2(t)$ vs. H_A : $S_1(t) \ge S_2(t)$, where $S_i(t)$ is the distribution of overall survival times for patients in arm i.

The Cox proportional hazard regression model will be used to determine hazard ratios and 95% confidence intervals for the treatment difference in overall survival. Unadjusted ratios and ratios adjusted for stratification variables and other covariates of interest will be computed.

11.5.2 Quality of Life (Functional Assessment of Cancer Therapy-L):

Patient-reported functional status will be assessed with the lung cancer subscales of the Functional Assessment of Cancer Therapy-Lung (FACT-L). The FACT-L is a 36-item questionnaire that uses 5-point Likert-type response choices (0 = not at all; 1 = a little bit; 2 = somewhat; 3 = quite a bit; 4 = very much). It will take less than 10 minutes to complete the questionnaire. The Trial Outcome Indices (TOI) also will be utilized to measure the summed functional well-being, physical well-being, and the additional concerns (lung symptom module) subscales of the FACT-L. A 5-point deterioration in the FACT-L TOI between pre-treatment and at year 1 will be considered clinically significant. The patient-reported endpoint will be a difference in the deterioration from the pre-induction FACT-L TOI score to the score at 6-month post-treatment. This score measures functional status and a difference of 5 FACT-L TOI points will be considered clinically significant.[33]

The first analysis of change in QOL from baseline to 6 months will only be performed on patients who are still alive at 6 months. Changes in QOL will be also analyzed using all available data at baseline, 6, and 12 months with generalized estimating equations (GEE). We will also compare the percentage of patients in each arm with an effect size for the change in FACT-L TOI scores between pre-induction and 6 months of < .2; this will allow us to compare the percentage of patients in each arm whose functional status remains more similar to baseline levels.

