L2	I have been coughing	0	1	2	3	4
B5	I am bothered by hair loss	0	1	2	3	4
C6	I have a good appetite	0	1	2	3	4
L3	I feel tightness in my chest	0	1	2	3	4
L4	Breathing is easy for me	0	1	2	3	4
Q3	Have you ever smoked? No Yes If yes:					
L5	I regret my smoking	0	1	2	3	4

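### The lung cancer subscale is defined as nine lung symptom items, but two of the nine on the form are hair loss and smoking regret, and never-smokers are not asked the second

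*Combined protocol and SAP*

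**What the plan says.** Section 9.9 describes the subscale in one sentence: "The lung cancer sub-scale (LCS) consists of 9 items, involving lung cancer specific symptoms". On the response format it adds: "All items are rated on a 5 item (point) Likert Scale, from 0 (not at all) to 4 (very much". It then sets the threshold, "Thus, a difference of 3 LCS points will be considered clinically significant", and gives the LCS first place among the quality-of-life measures: "symptoms, this will be used for the primary endpoint; however, the more general subscales of physical and functional well-being" are to be collected as well. The same section builds the TOI by adding the physical, functional and lung cancer subscales. Section 11.5.2 uses that TOI, with a 5-point threshold, for the change from before treatment to 6 months after it. Section 11.5.2 also gives the length of the instrument: "The FACT-L is a 36-item questionnaire that uses 5-point Likert-type response choices".

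The Additional Concerns block of the Appendix VIII worksheet contains "I am bothered by hair loss" (B5) and "I regret my smoking" (L5). L5 follows a screening question and is put only to patients who have smoked. Item 8 of the eligibility checklist records smoking status, with never as a permitted answer, and excludes nobody on it.

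On treatment, section 7.0 says that "chemotherapy may be administered concurrently ONLY to patients enrolled on the standard arm (30 fractions"), as carboplatin and paclitaxel. Sections 3.1.9 and 7.0 allow chemotherapy before or after radiotherapy in either arm.

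**The concern.** The stated item set does not match its stated purpose. A score presented as lung cancer symptoms includes one item about hair and one about regret over smoking. L5 has no reason to respond to the radiation schedule. B5 may respond to treatment, but not through the lungs. Both dilute a score meant to register what section 9.9 expects from hypofractionation, namely effects such as pneumonitis and oesophagitis.

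The definition also cannot be applied to everyone. A never-smoker has no nine-item score, and neither section says what to do with the missing item. Two analysts could treat it as zero, prorate it or drop the patient, and each would follow the text as written. The LCS is part of the TOI, so the main measure of 9.9 and the endpoint of 11.5.2 are both affected.

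**Working it through.** **1. Reproduce the plan's counts.** The Additional Concerns items in Appendix VIII are B1, C2, L1, L2, B5, C6, L3, L4 and L5, which makes 9. The smoking screening question is not scored 0-4 and is not counted. Whole form: physical 7 + social 7 + emotional 6 + functional 7 + 9 = 36. Both stated figures (9 and 36) are reproduced, but only with B5 and L5 included.

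**2. Ranges, at 4 points per item.**

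| Items scored | LCS maximum | TOI maximum |
|---|---|---|
| All nine (ever-smoker) | 9 × 4 = 36 | (7 + 7 + 9) × 4 = 92 |
| Without L5 (never-smoker) | 8 × 4 = 32 | (7 + 7 + 8) × 4 = 88 |
| Without B5 and L5 | 7 × 4 = 28 | (7 + 7 + 7) × 4 = 84 |

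B5 and L5 together hold 8/36 = 22% of the nine-item LCS range. Either one alone can move a single patient by 4 points, more than the 3-point threshold. That is an individual extreme, not a difference between arm means.

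**3. Never-smokers.** L5 is absent at every visit, so it contributes nothing to the raw change from baseline. The level still differs (maximum 32 against 36). If the score is prorated to nine items, each never-smoker's LCS change is multiplied by 9/8 = 1.125.

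**4. Hair loss and concurrent chemotherapy.** The shift in the between-arm LCS mean is p × d. Here p is the extra share of Arm B exposed through concurrent treatment, and d is the mean worsening of B5 in those patients. The documents give neither, nor do they say that this chemotherapy causes hair loss, so all three are assumptions.

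| p | d = 1 | d = 2 | d = 3 | d = 4 |
|---|---|---|---|---|
| 0.10 | 0.10 | 0.20 | 0.30 | 0.40 |
| 0.25 | 0.25 | 0.50 | 0.75 | 1.00 |
| 0.50 | 0.50 | 1.00 | 1.50 | 2.00 |
| 0.75 | 0.75 | 1.50 | 2.25 | 3.00 |

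For d = 2 and p from 0.10 to 0.60, the shift is 0.2 to 1.2 points. Against the 3-point LCS threshold that is 0.2/3 = 7% to 1.2/3 = 40%. Against the 5-point TOI threshold it is 4% to 24%. In the table, 3 points is reached only at p = 0.75 with d = 4.

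**5. Timing.** The worksheet asks about the past 7 days, and concurrent chemotherapy is given during radiation. A hair-loss effect is therefore most plausible at the end-of-treatment assessment. The main contrast in 11.5.2 is at 6 months, and its GEE analysis uses baseline, 6 and 12 months.

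**6. Thresholds.** Three points is 3/36 = 8.3% of a nine-item range and 3/28 = 10.7% of a seven-item range. Five points is 5/92 = 5.4% or 5/84 = 6.0% of the TOI. Section 9.9 takes its 3 points from the FACT-G subscales, which on this form have 6 or 7 items (maximum 24 or 28).

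**The case against.** The strongest reply is that this is a validated, cited instrument, that its standard scoring is implied, and that the endpoint is a change score in which L5 drops out. The cancellation stands for raw change. The appeal to standard scoring does not settle the item set, because the only instruction the plan gives is nine items and no scoring key is supplied.

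Three stronger readings are tempting, and the documents do not support them.

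- **That the plan sets chemotherapy in Arm B against none in Arm A, so that hair loss biases quality of life towards Arm A.** Only concurrent use is confined to Arm B; sequential and adjuvant chemotherapy are open to both arms. The documents never attribute hair loss to chemotherapy. Section 1.1, which lists toxicities of the common regimens, does not mention it, and section 6.9.1 lists alopecia as an effect of radiation. A shift is possible under a stated assumption but is not established.
- **That raw answers are to be added without reversing the unfavourable items.** Section 9.9 describes response options, and the summing in 9.9 and 11.5.2 is of subscales. The plan is silent on reversal; it does not instruct the error.
- **That hair loss alone could produce a clinically significant lung-symptom difference.** The assumed range of 0.2 to 1.2 points reaches neither threshold.

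A fair objection to the remedy is that C2 (weight), C6 (appetite) and L1 (clear thinking) are not obviously lung symptoms either. The documents alone show that B5 and L5 do not fit; they do not prove that the other seven are the correct set. The remedy therefore includes a check against the scoring manual.

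**Conclusion.** The point holds in a limited form. The nine-item definition in section 9.9 includes two items that are not lung symptoms, worth 22% of the range, and it cannot be computed for eligible never-smokers. Both facts follow from counting the form and need no assumption. For never-smokers the consequence is a lower maximum (by 4 points on either scale) and, under prorating, a 12.5% inflation of LCS change; raw change is unaffected.

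The hair-loss effect on the comparison of arms is conditional. It needs concurrent carboplatin and paclitaxel to worsen B5, and it depends on how many Arm B patients receive them. Under the ranges shown it is a fraction of the 3-point threshold, and it is less likely at 6 months than at the end of treatment.

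Quality of life is a secondary endpoint. Overall survival and the sample size are unchanged.

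**What to change.** In sections 9.9 and 11.5.2:

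- Replace the nine-item LCS with B1, C2, L1, L2, C6, L3 and L4, scored so that higher is better (range 0-28).
- Build the TOI from these seven plus the physical and functional items (21 items, range 0-84).
- Report B5 and L5 separately, with L5 among ever-smokers only.
- Before analysis, check the item set, and the 3-point LCS and 5-point TOI thresholds, against the instrument's scoring manual, and record the result.

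The cost is a change of scoring wording. The worksheet, the visit schedule and data already collected stay as they are, since all nine items are still recorded.

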10.0 Data Collection

Patient, treatment, HRQOL, and patient perspective costs data (Appendix VII) should be submitted to:

Department of Radiation Oncology
Clinical Research Office
The University of Texas Southwestern Medical Center
Attention: [name], Project Manager
[name]
[name]
[contact]

Economic data (patient bills, and other cost documents) will be collected by:

Department of Epidemiology and Biostatistics School of Rural Public Health Texas A&M Health Science Center, [name]

Attn: [name] [name] [name]

Patients will be identified only by initials (first middle last) and a unique study ID number assigned to each study participant; if there is no middle initial, a hyphen will be used (first-last). Last names with apostrophes will be identified by the first letter of the last name. Identifiable information will be released to Drs. [name] and [name] at Department of Epidemiology and Biostatistics, Texas A&M Health Science Center (TAMHSC) for obtaining the bills that are associated with each service reported in the case report forms.

Item	Due
Demographics	Within 2 weeks of study enrollment
Eligibility and Entry Characteristics, including baseline H&P and Zubrod PS	Within 2 weeks of study enrollment
Pathology Report	Within 2 weeks of study enrollment
Follow-up H&P data	At post XRT follow-up at 1, 3, 6, 9, and 12 months, then q 4 months year 2, then q6 months years 3-5; then annually
Tumor response evaluation	At post XRT follow-up at 3, 6, 9, and 12 months, then q 4 months year 2, then q6 months years 3-5; then annually
Adverse Event assessment	After each weekly treatment visit, then post XRT follow-up at 1, 3, 6, 9, and 12 months, then q 4 months year 2, then q6 months years 3-5; then annually
Healthcare Utilization/Cost Worksheet (Appendix VI),	Within 2 weeks of study enrollment, at the end of treatment, and at post treatment follow up at 1, 3, 6, 9, and 12 months, then q 4 months year 2, then q6 months years 3-5; then annually until death
FACT-L (Appendix VIII), EQ-5D (Appendix IX)	Within 2 weeks of study enrollment, at the end of treatment, and at post treatment follow up at 6 and 12 months,
Patient Perspective Cost Assessment (Appendix VII)	Upon radiation completion or first possible post treatment follow up (1 month). To be administered just once.

Data collection for QA

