6.0 Radiation Therapy

6.1 Dose Specifications for Radiation Therapy for Arm A

Protocol treatment must begin within 4 weeks after patient registration/study enrollment to the trial. Simulation can take place before registration/study enrollment, but treatment must begin within 3 weeks of completion of simulation.

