12.3 Registration/Randomization Procedure

All subjects must be registered with the Radiation Oncology before enrollment to study. Prior to registration, eligibility criteria must be confirmed with the Radiation Oncology Study Coordinator. To register a subject, call [name] Monday through Friday, 9:00AM-5:00PM

Each newly consented subject should be numbered using the schema provided above. Upon registration, the registrar will assign the additional registration/randomization code according to the numbering schema outlined above, which should then be entered as the patient study id in Velos upon updating the status to enrolled.

The numbering schema should clearly identify the site number; the sequential number of the subject enrolled as well as the status of the subjects enrolled so that the number of subjects consented versus the number of subjects actually enrolled may be easily identified.

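### The baseline FACT-L and EQ-5D need only precede radiation, not randomization, so in this unmasked trial they may be self-reported after the patient knows the arm

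*Combined protocol and SAP*

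**What the plan says.** **When the baseline forms are completed.** Section 9.9 sets four quality-of-life time points: "baseline (pretreatment), at the end of treatment (last day of treatment), and at the 6 and 12 month follow ups". Appendix II marks the first FACT-L and EQ-5D in the column for the period before radiation. Its pre-registration column, which holds the physical examination, Zubrod status, weight, lung function and comorbidity index, is blank for these forms. Section 4.1 lists the tests required before enrollment and includes no questionnaire. Item 9 of the eligibility checklist and section 3.1.10 enforce only the section 4 evaluations.

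**When the data are due.** Section 10.0 opens with "Patient, treatment, HRQOL, and patient perspective costs data (Appendix VII) should be submitted to" and then gives a table of items and due dates. The FACT-L and EQ-5D row reads "Within 2 weeks of study enrollment, at the end of treatment, and at post treatment follow up at 6 and 12 months".

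**When the arm is assigned.** Section 12.3: "Upon registration, the registrar will assign the additional registration/randomization code". Section 6.1: "Protocol treatment must begin within 4 weeks after patient registration/study enrollment to the trial". Section 6.2 repeats the 4-week limit for Arm B. Arm A receives 15 fractions and Arm B 30-33. No masking of patients is described.

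**How the baseline is used.** Section 11.5.2 defines the patient-reported endpoint as "a difference in the deterioration from the pre-induction FACT-L TOI score" to the score 6 months after treatment. The same section also says "A 5-point deterioration in the FACT-L TOI between pre-treatment and at year 1 will be considered clinically significant", and elsewhere calls the first score simply baseline.

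**The concern.** A baseline supports a randomized comparison of change because it is measured before anything can differ by arm. Here the measure is self-reported, the arms are visibly different, and the only stated condition is that the form comes before radiation. A patient told to expect about three weeks of treatment and a patient told to expect six or more may answer the same items differently, before either has been treated. Any such difference would enter the change score as if it were an effect of treatment on quality of life.

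The second route is missing data. Section 11.5 keeps every eligible randomized patient in the comparison regardless of compliance. A patient who refuses the assigned arm before filling in the form has no baseline, and so cannot contribute a change score even if follow-up continues, as section 9.5.1 allows. If refusal differs by arm, so does the set of patients with a baseline.

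Quality of life is the first secondary endpoint listed in section 11.1.2. A baseline not taken before allocation cannot be recovered at analysis.

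**Working it through.** There is no planned figure to reproduce. The check is of the order of events, followed by how a baseline shift would travel through the analysis.

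**1. Order of events at a site that follows every section**

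| Step | Earliest | Latest | Source |
|---|---|---|---|
| Consent and section 4.1 tests | before registration | registration | 3.1.8, 3.1.10, 4.1 |
| Arm assigned | registration (week 0) | registration | 12.3 |
| Radiation starts | week 0 | week 4 | 6.1, 6.2 |
| Baseline FACT-L and EQ-5D | not stated | start of radiation | 9.9, Appendix II |

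The only upper limit on the baseline forms is the start of radiation. The interval in which the arm is known but the forms may still be outstanding therefore runs from 0 to 4 weeks. No section closes it.

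**2. Does section 10.0 close it?** No. Its 2 weeks are counted forward from enrollment, so they too allow completion after the arm is assigned.

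**3. Effect on a raw change score.** Let Y0 and Y6 be the mean TOI scores at baseline and 6 months. The comparison of change is

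D = (Y6_A − Y0_A) − (Y6_B − Y0_B).

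If knowing the arm moves the reported baseline by s_A in Arm A and s_B in Arm B, and leaves later scores alone, then

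D_observed = D − (s_A − s_B).

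A differential shift enters in full with its sign reversed; equal shifts cancel. The documents give no value for s_A or s_B, no standard deviation for the TOI and no expected direction, so D_observed − D cannot be evaluated.

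**4. Effect on the other analyses.** Section 11.5.2 also plans generalized estimating equations on the baseline, 6-month and 12-month scores, and a comparison of the percentage of patients with a small standardized change. Both use the same baseline. The section does not say whether baseline enters as an outcome or a covariate, so the share of any shift carried through is unknown.

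**5. EQ-5D.** Section 11.5.4 converts EQ-5D to utilities, interpolates between visits and integrates over survival time. The baseline is one end of the first interpolated interval, up to the end-of-treatment form. It is not subtracted from later values, so the algebra in step 3 does not apply to it.

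**The case against.** **The plan does require a pretreatment baseline.** A reader might infer from section 10.0 that a first form given after radiation has begun would comply, since radiation can start at once and 2 weeks are allowed. The documents do not support that. Section 9.9, Appendix II and section 11.5.2 all place the baseline before treatment. Section 10.0 concerns where and when data are sent, and the same 2 weeks apply to demographics and the pathology report. A form completed before radiation and submitted within 2 weeks satisfies every section. What remains is a drafting weakness: the due column also carries administration times, such as the end of treatment, so it should say which kind of date this is.

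**Completion after allocation is allowed, not required.** This is correct. Many sites may give the forms at the consent visit, so it does not follow that every comparison is contaminated.

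**The mechanism may be weak.** The TOI sums physical, functional and lung-symptom items and leaves out emotional well-being, and the items refer to the past 7 days. The 6- and 12-month answers are just as unmasked, so an earlier baseline does not cure open-label reporting. All of this stands. It limits what the fix can achieve, but it does not show that the baseline is safe from knowledge of the arm.

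**Pre-induction is only a slip.** Probably so, because section 11.5.2 uses two other terms for the same score. It can be corrected at the same time.

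**The Appendix II header is partly lost in the available text.** Some caution about its columns is fair. The conclusion does not depend on them alone: section 9.9 asks only for pretreatment completion, and section 4.1 lists no questionnaire.

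**Conclusion.** The point holds in a limited form. No section requires the baseline FACT-L or EQ-5D before randomization. Allocation occurs at registration, up to 4 weeks may pass before radiation, and the patient will know the arm. A fully compliant baseline can therefore be given after allocation, and some randomized patients may have none. This can bias the secondary change-from-baseline comparisons in section 11.5.2. It has less bearing on quality-adjusted survival, where EQ-5D is integrated rather than differenced, and none on overall survival.

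The size and direction are unknown. One might assume a shift and divide it by the 5-point threshold in section 11.5.2, but the result would only restate the assumption.

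The conclusion assumes that patients are told their arm soon after registration, and that at least some sites leave the forms until after that. The documents permit both but do not show how often either happens. The change is worth making because it removes an avoidable weakness at almost no cost.

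**What to change.** - **Appendix II and section 4.1:** require the baseline FACT-L and EQ-5D after consent and before the randomization code is assigned, within a short window before registration, for example 14 days (the window section 4.1.2 already uses for the pregnancy test). Listing them in section 4.1 brings them under checklist item 9. They should not simply move to the existing 12-week column: with radiation starting up to 4 weeks after registration, the baseline could then precede treatment by 12 + 4 = 16 weeks. With a 14-day window the maximum is 2 + 4 = 6 weeks.
- **Section 10.0:** state that the 2 weeks from enrollment is the submission limit for a form already completed before randomization.
- **Section 11.5.2:** use pre-randomization baseline in place of pre-induction, and use that one term throughout.

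The Appendix VI cost worksheet can stay where it is. It records health-care use over the prior year, and there is no clear reason why knowing the arm would alter it.

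**Cost:** wording in four places and an earlier slot for two existing forms, with no added assessment. The downside is that the baseline lies slightly further from the start of radiation. Because chemotherapy is excluded only in the last week before registration, a form completed early in a 14-day window could still reflect recent chemotherapy. Recording the completion date would let this be described.
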